6.3.3 Activity

There are no study specific restrictions.

6.4 Screen Failures

Screen failures are defined as participants who consent to participate in the clinical study but are not subsequently entered in the study. A minimal set of screen failure information is required to ensure transparent reporting of screen failure participants to meet the Consolidated Standards of Reporting Trials (CONSORT) publishing requirements and to respond to queries from regulatory authorities. Minimal information includes demography, screen failure details, eligibility criteria, and any adverse events or serious adverse events (SAE) meeting reporting requirements as outlined in the entry guidelines.

6.5 Participant Replacement Strategy

If a participant withdraws from the trial, a replacement participant may be enrolled if deemed appropriate by the investigator and Sponsor. The replacement participant will generally receive the same treatment or treatment sequence (as appropriate) as the participant being replaced. The replacement participant will be assigned a unique treatment number. The trial site should contact the Sponsor for the replacement participant's treatment number.

Please see Section 5.1.4 regarding replacement of participants during the DLT period.

7. Treatments

Study treatment is defined as any investigational treatment(s), marketed product(s), placebo, or medical device(s) intended to be administered to a study participant according to the study protocol.

Clinical supplies [study treatment(s) provided by the Sponsor] will be packaged to support enrollment and replacement participants as required. When a replacement participant is required, the Sponsor or designee needs to be contacted prior to dosing the replacement supplies. Clinical supplies will be affixed with a clinical label in accordance with regulatory requirements.

7.1 Treatments Administered

The study treatment(s) to be used in this trial are outlined below in [Table 5](#).

Table 5 Study Treatment(s)

Study Treatment Name		Dosage Formulation	Unit Dose Strength(s)	Dosage Level(s)	Route of Administration	Sourcing
Pembrolizumab (MK-3475)		Solution for Infusion	100 mg/4 mL	200 mg Q3W	IV infusion	Provided centrally by the Sponsor
Binimetinib		Tablet	15 mg	30 mg BID 45 mg BID	Oral	Provided centrally by the Sponsor
mFOLFOX7	Oxaliplatin	Solution Infusion	5 mg/mL	85 mg/m ² Q2W	IV infusion	Provided centrally by the Sponsor or locally by the trial site, subsidiary, or designee
	Leucovorin (Calcium Folinate)	Solution Injection		70 mg/m ² Q2W		
	5-FU	Solution Injection	50 mg/mL	400 mg/m ² Q2W		
				2400 mg/m ² Q2W		
				2000 mg/m ² Q2W		
	Irinotecan	Solution Infusion	20 mg/mL	180 mg/m ² Q2W		
FOLFIRI	Leucovorin (Calcium Folinate)	Solution Injection		150 mg/m ² Q2W		
	5-FU	Solution Injection	50 mg/mL	400 mg/m ² Q2W	IV infusion	Provided centrally by the Sponsor or locally by the trial site, subsidiary, or designee
				2400 mg/m ² Q2W		
				2000 mg/m ² Q2W		

Abbreviations: BID=twice daily; FOLFIRI = (irinotecan [180 mg/m²]; leucovorin [calcium folinate] [400 mg/m²]; 5-FU 2400 mg/m²); mFOLFOX7 = (oxaliplatin [85 mg/m²]; leucovorin [calcium folinate] [400 mg/m²]; 5-FU 2400 mg/m²); 5-FU=Fluorouracil; IV=intravenous; Q2W= every 2 weeks; Q3W=every 3 weeks.

All supplies indicated in [Table 5](#) will be provided per the ‘Sourcing’ row depending upon local country operational requirements. Every attempt should be made to source these supplies from a single lot/batch number. The trial site is responsible for recording the lot number, manufacturer, and expiry date for any locally purchased product as per local guidelines unless otherwise instructed by the Sponsor.

Refer to section 9.1.8 for details regarding administration of the study treatment.

7.2 Dose Modification (Escalation/Titration/Other)

7.2.1 Guideline for Dose Modification

Guidelines for dose delay and dose modification are described below and are applicable to the start of each cycle as well as during the cycle if treatment-related toxicities occur. If treatment-related toxicities occur that require supportive care including steroid use follow the general recommendations in Section 7.7.1 - Rescue Medications & Supportive Care.

Dosing interruptions are permitted after Cycle 1 in the case of medical/surgical events or logistical reasons not related to study therapy (eg, elective surgery, unrelated medical events, participant vacation, and/or holidays). Participants should be placed back on study therapy within 3 weeks of the scheduled interruption, unless otherwise discussed with the Sponsor. The reason for interruption should be documented in the participant’s study record.

7.2.1.1 Dose Modification Due to Adverse Events

The CTCAE Version 4.0 must be used to grade the severity of adverse events. The Investigator may attribute each toxicity event to pembrolizumab alone, binimatinib alone, or to any of the components of the standard of care chemotherapies (mFOLFOX7 and FOLFIRI), or to any component of the combination therapy, and follow corresponding dose modification guidelines described in Section 7.2.1.2 to Section 7.2.1.5.

If a participant experiences overlapping toxicities that may be attributed to the combination regimen as a whole rather than to a single drug, Investigators should consider dose reduction/interruption/discontinuation of all the drugs in the combination, in addition to considering the discontinuation of the drug that most likely causes the toxicities, and/or consult with the Sponsor. Early recognition of immune related adverse effect and initiation of systemic corticosteroids is critical to reduce the risk of complications. Investigators should follow individual guidelines described in [Table 6](#) (pembrolizumab), [Table 7](#) (binimatinib), Section 7.2.1.4 (mFOLFOX7), or Section 7.2.1.5 (FOLFIRI), respectively, and/or consult with the Sponsor, to determine whether and when to resume the withheld/interrupted drug(s).

All AEs should be followed as clinically appropriate until stabilization or resolution.

The drug to which the investigator is attributing to the AE must be documented (AE eCRF, patient notes, etc.).

Exceptional circumstances to following the dose modification tables below should be consulted with the Sponsor.

7.2.1.2 Immune-Related Events and Dose Modification (Withhold, Treat, Discontinue)

Dose Modification and Toxicity Management for Immune-related AEs Associated with Pembrolizumab

AEs associated with pembrolizumab exposure may represent an immune-related response. These irAEs may occur shortly after the first dose or several months after the last dose of pembrolizumab treatment and may affect more than one body system simultaneously. Therefore, early recognition and initiation of treatment is critical to reduce complications. Based on existing clinical study data, most irAEs were reversible and could be managed with interruptions of pembrolizumab, administration of corticosteroids and/or other supportive care. For suspected irAEs, ensure adequate evaluation to confirm etiology or exclude other causes. Additional procedures or tests such as bronchoscopy, endoscopy, skin biopsy may be included as part of the evaluation. Based on the severity of irAEs, withhold or permanently discontinue pembrolizumab and administer corticosteroids.

Dose Modification and Toxicity Management Guidelines for irAEs associated with pembrolizumab monotherapy, coformulations, or IO combinations are provided in [Table 6](#).

See Section 7.7.1.4 for supportive care guidelines, including the use of corticosteroids.

Table 6 Dose Modification and Toxicity Management Guidelines for Immune-related Adverse Events Associated with Pembrolizumab Monotherapy, Coformulations or IO Combinations

General instructions:				
irAEs	Toxicity Grade (CTCAEv4.0)	Action With Pembrolizumab Monotherapy, Coformulations or IO Combinations	Corticosteroid and/or Other Therapies	Monitoring and Follow-up
Pneumonitis	Grade 2	Withhold	
 Administer corticosteroids (initial dose of 1-2 mg/kg prednisone or equivalent) followed by taper 	
 Monitor participants for signs and symptoms of pneumonitis Evaluate participants with suspected pneumonitis with radiographic imaging and initiate corticosteroid treatment Add prophylactic antibiotics for opportunistic infections
	Recurrent Grade 2 or Grade 3 or 4	Permanently discontinue		
Diarrhea / Colitis	Grade 2 or 3	Withhold	
 Administer corticosteroids (initial dose of 1-2 mg/kg prednisone or equivalent) followed by taper 	
 Monitor participants for signs and symptoms of enterocolitis (ie, diarrhea, abdominal pain, blood or mucus in stool with or without fever) and of bowel perforation (ie, peritoneal signs and ileus) Participants with \geqGrade 2 diarrhea suspecting colitis should consider GI consultation and performing endoscopy to rule out colitis Participants with diarrhea/colitis should be advised to drink liberal quantities of clear fluids. If sufficient oral fluid intake is not feasible, fluid and electrolytes should be substituted via IV infusion.
	Recurrent Grade 3 or Grade 4	Permanently discontinue		

irAEs	Toxicity Grade (CTCAEv4.0)	Action With Pembrolizumab Monotherapy, Coformulations or IO Combinations	Corticosteroid and/or Other Therapies	Monitoring and Follow-up
AST / ALT Elevation or Increased Bilirubin	Grade 2	Withhold	
 Administer corticosteroids (initial dose of 0.5-1 mg/kg prednisone or equivalent) followed by taper 	
 Monitor with liver function tests (consider weekly or more frequently until liver enzyme value returned to baseline or is stable)
	Grade 3 or 4	Permanently discontinue	
 Administer corticosteroids (initial dose of 1-2 mg/kg prednisone or equivalent) followed by taper 	
T1DM or Hyperglycemia	New onset T1DM or Grade 3 or 4 hyperglycemia associated with evidence of β -cell failure	Withhold ^a	
 Initiate insulin replacement therapy for participants with T1DM Administer anti-hyperglycemic in participants with hyperglycemia 	
 Monitor participants for hyperglycemia or other signs and symptoms of diabetes
Hypophysitis	Grade 2	Withhold	
 Administer corticosteroids and initiate hormonal replacements as clinically indicated 	
 Monitor for signs and symptoms of hypophysitis (including hypopituitarism and adrenal insufficiency)
	Grade 3 or 4	Withhold or permanently discontinue ^a		
Hyperthyroidism	Grade 2	Continue	
 Treat with non-selective beta-blockers (eg, propranolol) or thionamides as appropriate 	
 Monitor for signs and symptoms of thyroid disorders
	Grade 3 or 4	Withhold or Permanently discontinue ^a		

irAEs	Toxicity Grade (CTCAEv4.0)	Action With Pembrolizumab Monotherapy, Coformulations or IO Combinations	Corticosteroid and/or Other Therapies	Monitoring and Follow-up
Hypothyroidism	Grade 2-4	Continue	
 Initiate thyroid replacement hormones (eg, levothyroxine or liothyronine) per standard of care 	
 Monitor for signs and symptoms of thyroid disorders
Nephritis and renal dysfunction	Grade 2	Withhold	
 Administer corticosteroids (prednisone 1-2 mg/kg or equivalent) followed by taper 	
 Monitor changes of renal function
	Grade 3 or 4	Permanently discontinue		
Myocarditis	Grade 1	Withhold	
 Based on severity of AE administer corticosteroids 	
 Ensure adequate evaluation to confirm etiology and/or exclude other causes
	Grade 2, 3 or 4	Permanently discontinue		
All Other irAEs	Persistent Grade 2	Withhold	
 Based on severity of AE administer corticosteroids 	
 Ensure adequate evaluation to confirm etiology or exclude other causes
	Grade 3	Withhold or discontinue ^b		
	Recurrent Grade 3 or Grade 4	Permanently discontinue		

AE(s)=adverse event(s); ALT= alanine aminotransferase; AST=aspartate aminotransferase; CTCAE=Common Terminology Criteria for Adverse Events; DRESS=Drug Rash with Eosinophilia and Systemic Symptom; GI=gastrointestinal; IO=immuno-oncology; ir=immune related; IV=intravenous; SJS=Stevens-Johnson Syndrome; T1DM=type 1 diabetes mellitus; TEN=Toxic Epidermal Necrolysis; ULN=upper limit of normal.

Note: Non-irAE will be managed as appropriate, following clinical practice recommendations.

^a The decision to withhold or permanently discontinue pembrolizumab monotherapy, coformulations or IO combinations is at the discretion of the investigator or treating physician. If control achieved or \leq Grade 2, pembrolizumab monotherapy, coformulations or IO combinations may be resumed.

^b Events that require discontinuation include, but are not limited to: Guillain-Barre Syndrome, encephalitis, myelitis, DRESS, SJS, TEN and other clinically important irAEs (eg, vasculitis and sclerosing cholangitis).

7.2.1.3 Binimetinib

The starting dose level for binimetinib is 30 mg BID, and a dose reduction below 30 mg BID is not allowed. Participants requiring additional reductions must discontinue binimetinib treatment. Dose interruptions of more than 21 days are not allowed. In the cases of the dose interruption of longer than 21 days due to an AE, discontinuation of binimetinib should be considered.

For participants who do not tolerate the 45 mg BID dosing schedule, dose adjustment to 30 mg BID is permitted in order to allow the participant to continue on study drug.

Missed/skipped doses will not be made up (ie, the participant should not double their dose if the previous dose was missed). When the toxicity that resulted in a dose reduction improves to and remains stable at Grade 1 or less for a minimum of 21 days, the dose can be re-escalated at the investigators discretion provided there are no other concomitant toxicities.

No dose re-escalation of binimetinib is allowed after dose reduction due to left ventricular dysfunction or prolonged QTcF ≥ 501 msec.

No dose re-escalation of binimetinib is allowed after a dose reduction due to retinal toxicity \geq Grade 2.

Dose reduction/interruption/discontinuation decisions should be based on the CTCAE grade of the toxicity and the guidelines provided below. In general, doses should not be reduced or interrupted for Grade 1 toxicities, but treatment to control symptoms should be provided as appropriate.

Please refer to [Table 7](#) for dose adjustment recommendations for binimetinib-induced toxicities.

Table 7 Dose Modification Guideline for Binimatinib

Toxicity	Dose Adjustment for Binimatinib
Eye disorders- Retinal Events (including serous detachment of the retina)	
Grade 1	Maintain dose level of binimatinib and repeat ophthalmic monitoring including visual acuity assessment and ocular coherence tomography (OCT) within 10 days.
Grade 2	Interrupt binimatinib dosing and refer the participant to ophthalmologist within 1 week and obtain OCT within 10 days: 
 • If resolved to baseline or Grade ≤ 1 within 10 days, resume treatment at current dose level and continue schedule of visual assessments established per protocol. • If not resolved to baseline or Grade ≤ 1 within 10 days, resume treatment at reduced dose level and continue the schedule of events of visual assessments established per protocol.
Grade 3	Interrupt binimatinib and refer the participant to ophthalmologist within 1 week and obtain OCT: 
 • If resolved to baseline or Grade ≤ 2 within 7 days, resume treatment at current dose level and continue schedule of visual assessments established per protocol. • If not resolved to baseline or Grade ≤ 2 within 7 days, continue to hold the binimatinib dose and repeat ophthalmic assessment in 10 days. 
 ◦ If resolved to baseline or Grade ≤ 2, resume treatment at reduced dose level and continue schedule of visual assessments established per protocol. ◦ If remains Grade 3, permanently discontinue binimatinib.
Grade 4	Permanently discontinue binimatinib and immediately follow up with ophthalmic monitoring.
Eye disorder - RVO	
Any Grade	Permanently discontinue binimatinib.
Other eye disorders (i.e. Non-retinal Events)	
Grade 1-2	Maintain dose level of binimatinib and increase frequency of ophthalmic monitoring to at least 14 days until stabilization or resolution.
Grade 3	Interrupt binimatinib and refer participant to ophthalmologist within 1 week: 
 • If resolved to Grade ≤ 1 in ≤ 21 days, reduce 1 dose level of binimatinib. • If not resolved to Grade ≤ 1 in ≤ 21 days, permanently discontinue binimatinib.
Grade 4	Permanently discontinue binimatinib.

Toxicity	Dose Adjustment for Binimetinib
Liver-related adverse events	
Grade 1 AST or ALT ($>$ ULN - 3 x ULN)	Maintain dose level of binimetinib.
Grade 2 AST or ALT ($>$ 3 - 5.0 x ULN or 3 x baseline value) AND blood bilirubin \leq 2.0 x ULN	
Interrupt dose of binimetinib until resolved to Grade \leq 1 (or Grade \leq 2 in case of liver metastasis), then:
 
 • If resolved in \leq 14 days, maintain dose level of binimetinib. • If resolved in $>$ 14 days, reduce dose level of binimetinib. 
Recurrence:
 
 • Interrupt dosing of binimetinib until resolved to Grade \leq 1 (or Grade \leq 2 in case of liver metastasis), then resume treatment at a reduced dose.
Grade 2 AST or ALT ($>$ 3 - 5.0 x ULN or 3 x baseline value) AND blood bilirubin $>$ 2.0 x ULN	
Interrupt dose of binimetinib until resolved to Grade \leq 1 (or Grade \leq 2 in case of liver metastasis), then:
 
 • If resolved in \leq 7 days, resume treatment at a reduced dose of binimetinib. • If not resolved in \leq 7 days, permanently discontinue binimetinib.
Grade 3 AST or ALT ($>$ 5.0 - 8.0 x ULN) AND blood bilirubin \leq 2.0 x ULN	
Interrupt dose of binimetinib until resolved to Grade \leq 1 (or Grade \leq 2 in case of liver metastasis), then:
 
 • If resolved in \leq 14 days, maintain dose level of binimetinib. • If resolved in $>$ 14 days, reduce dose level of binimetinib. 
Recurrence:
 
 • Interrupt dosing of binimetinib until resolved to Grade \leq 1 (or Grade \leq 2 in case of liver metastasis), then resume treatment at a reduced dose.
AST or ALT ($>$ 8 x ULN) AND blood bilirubin* \leq 2.0 x ULN	Permanently discontinue binimetinib.
AST or ALT ($>$ 5.0 x ULN) AND blood bilirubin* $>$ 2.0 x ULN	Permanently discontinue binimetinib.
AST or ALT Grade 4 ($>$ 20.0 x ULN)	Permanently discontinue binimetinib.

Toxicity	Dose Adjustment for Binimetinib
Cardiac disorders	
Left ventricular systolic dysfunction Asymptomatic decrease of >10% in LVEF compared to baseline and the LVEF is below the institution's lower limit of normal	
Interrupt dose of binimetinib and repeat evaluation of LVEF within 2 weeks.
 
 • If the LVEF recovers (defined as LVEF \geq 50% or \geq LLN and absolute decrease \leq 10% compared to baseline) \leq 3 weeks, reduce 1 dose level after approval of the Sponsor Medical Monitor. Monitor LVEF 2 weeks after restarting on binimetinib, every 4 weeks for 12 weeks and subsequently as per protocol. • If the LVEF does not recover within 3 weeks, permanently discontinue participant from study treatment. Closely monitor LVEF until resolution (or 16 weeks).
Grade 3-4	Permanently discontinue participant from binimetinib. Closely monitor LVEF until resolution (or 16 weeks).
CK elevation	
Grade 1-2	
Continue treatment on same dose level. Ensure patient is adequately hydrated. Monitor closely CK and serum creatinine levels.
 
(If total CK \geq 3 X ULN, measure isoenzymes and myoglobin in blood and urine).

Grade 3 ($> 5.0 - 10.0 \times$ ULN) without renal impairment (ie, serum creatinine $< 1.5 \times$ ULN or 1.5 x baseline)	
If asymptomatic, maintain dose of binimetinib. Monitor closely and measure isoenzymes and myoglobin in blood and urine.
 
If symptomatic (muscle pain/spasms or muscle weakness), interrupt dose of binimetinib until resolved to CTCAE Grade \leq 1 and monitor closely, then:
 
 • If resolved in \leq 21 days, reduce 1 dose level of binimetinib. • If resolved in $>$ 21 days, permanently discontinue binimetinib.
Grade 4 without renal impairment (ie, serum creatinine $< 1.5 \times$ ULN or 1.5 x baseline)	
If asymptomatic, interrupt dose of binimetinib and monitor closely. Ensure patient is adequately hydrated and monitor and measure isoenzymes and myoglobin in blood or urine, and serum creatinine.
 
 • If resolved in \leq 21 days, reduce 1 dose level of binimetinib. • If resolved in $>$ 21 days, permanently discontinue binimetinib. 
If symptomatic, permanently discontinue binimetinib.
 
If symptomatic (muscle pain/spasms), permanently discontinue binimetinib.

Grade 3 or 4 with renal impairment (ie, serum creatinine $\geq 1.5 \times$ ULN or 1.5 x baseline)	
Interrupt binimetinib dose until resolved to Grade $<$ 1 or baseline level. Ensure patient is adequately hydrated. Monitor isoenzymes and myoglobin in blood or urine, and serum creatinine, then:
 
 • If resolved in \leq 21 days, reduce 1 dose level of binimetinib. • If resolved in $>$ 21 days, permanently discontinue binimetinib. 
Recurrence:
 
 • Permanently discontinue binimetinib

Toxicity	Dose Adjustment for Binimetinib
Rash	
Grade 1	Treatment with binimetinib should be maintained at the current dose. Initiate prophylactic regimen if it was not already and monitor closely.
Grade 2	
First occurrence: Treatment with binimetinib should be maintained at the current dose and rash should be closely monitored. Initiate prophylactic regimen if it was not already started.
 
Reassess within a maximum of 2 weeks. If rash worsens or does not improve, interrupt dosing until improvement to Grade \leq 1. Resume treatment at the same dose level.
 
Second occurrence: Reassess within a maximum of 2 weeks. If rash worsens or does not improve, interrupt dosing until improvement to Grade \leq 1. Resume treatment at a reduced dose level.
 
Only one dose reduction is permitted.

Grade 3	
First occurrence: Treatment with binimetinib should be interrupted. Reassess the participant weekly. Consider referral to dermatologist and manage rash per dermatologist's recommendation.
 
Interrupt treatment until improvement to Grade \leq 1. Resume treatment with binimetinib at the same dose level.
 
Second occurrence: Interrupt treatment until improvement to Grade \leq 1. Resume treatment with binimetinib at a reduced dose level. If participant is at the lowest dose, participant should be discontinued.
 
Consider referral to dermatologist and manage rash per dermatologist's recommendation.

Grade 4	Permanently discontinue binimetinib.
Diarrhea	
Uncomplicated Grade 1-2	Consider temporary interruption of binimetinib until resolved to Grade \leq 1. Treatment with binimetinib may then be resumed at the same dose level.
Complicated Grade 1-2	Temporarily interrupt binimetinib treatment until resolved to Grade \leq 1. Restart binimetinib at one reduced dose level. If participant is at the lowest dose, participant should be discontinued.
Grade 3-4	Temporarily interrupt binimetinib treatment until resolved to Grade \leq 1. Restart binimetinib at a reduced dose level. If participant is at the lowest dose, participant should be discontinued.
Nausea/Vomiting	
Grade 1-2	Treatment with binimetinib should be maintained at the current dose. Promptly institute antiemetic measure.
Grade 3	
Temporarily interrupt binimetinib treatment until resolved to Grade \leq 1. Resume treatment with binimetinib at the same dose if, in the judgment of the investigator, the toxicity is considered to be unrelated to binimetinib, or at one reduced dose level.
 
Note: Interrupt dose for \geq Grade 3 vomiting or Grade 3 nausea only if the vomiting or nausea cannot be controlled with optimal antiemetics (as per local practice).

Grade 4	Permanently discontinue binimetinib treatment

Toxicity	Dose Adjustment for Binimetinib
Interstitial lung disease/pneumonitis	
Grade 1	Maintain dose level of binimetinib. Monitor weekly.
Grade 2	Withhold binimetinib for up to 3 weeks. If improved to Grade 0 or 1, resume treatment at 1 reduced dose level of binimetinib. If not resolved within 3 weeks, permanently discontinue binimetinib.
Grade 3-4	Permanently discontinue binimetinib.
Venous Thromboembolism	
Uncomplicated DVT or PE	Withhold binimetinib for up to 3 weeks. • If improved to Grade 0 or 1, resume at reduced dose. If not improved, permanently discontinue.
Life threatening PE	Permanently discontinue binimetinib.
All other adverse events (suspected to be related)	
Grade 1-2	If the event is a persistent Grade 2 AE not responsive to a specific therapy, consider study drug interruption or reduction.
Grade 3	For other AEs, interrupt study drug until resolution to Grade ≤ 1 or to pre-treatment/baseline level. If the event resolves within 21 days then study drug may be restarted at a lower dose (one level below that previously received) based upon the Investigator's discretion.
Grade 4	Permanently discontinue study drug.

Abbreviations: AE=adverse event; ALT=alanine aminotransferase; AST=aspartate aminotransferase; BID=twice daily; CK=creatinine kinase; CTC=Common Terminology Criteria; ECG=electrocardiogram; LLN= lower limit of normal; LVEF=left ventricular ejection fraction; OCT= ocular coherence tomography; RVO=retinal vein occlusion; QTc=Q-T interval QTcF=QT interval calculated according to the Fridericia method; ULN= upper limit of normal.

7.2.1.4 mFOLFOX7

Dose delays and treatment restarts will be made at the discretion of the site investigator according to institutional guidelines or local standard practice. The recommended dose reduction is stepwise by 20%. Discontinuation of treatment should be considered if dose reduction below the following dosage is required: Oxaliplatin 50 mg/m² and 5-FU infusion 1600 mg/m² 46 to 48 hours.

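### Table 7 lets a Grade 3 retinal event restart binimetinib at the current dose while still Grade 2, which an event that began at Grade 2 may not do; and the pregnancy-reporting window in Section 9.3.1 ends before required contraception and conflicts with Section 9.3.6

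*Combined protocol and SAP*

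**What the plan says.** **Retinal events (Section 7.2.1.3, Table 7).** Both the Grade 2 and Grade 3 rows begin with a hold and referral to an ophthalmologist.

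- *Grade 3.* If the event is at baseline or Grade ≤2 "within 7 days, resume treatment at current dose level and continue schedule of visual assessments established per protocol". If it is still Grade 3 at day 7, the hold continues with a repeat examination in 10 days. Improvement to Grade ≤2 then leads to a reduced dose, and persistent Grade 3 to permanent discontinuation.
- *Grade 2.* The current dose resumes only at baseline or Grade ≤1 within 10 days. "If not resolved to baseline or Grade ≤ 1 within 10 days, resume treatment at reduced dose level".
- *Floor.* No dose below 30 mg BID is permitted: "Participants requiring additional reductions must discontinue binimetinib treatment".
- *Other limits.* "No dose re-escalation of binimetinib is allowed after a dose reduction due to retinal toxicity" of Grade 2 or higher. "Dose interruptions of more than 21 days are not allowed".

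**Pregnancy.** Section 6.1 (criteria 13 and 14) requires contraception for at least 180 days after the last dose, for men and women. Section 9.3.1 sets pregnancy reporting to 120 days after treatment stops, or 30 days if new anticancer therapy starts. After the follow-up period, Table 10 asks only for the outcome of pregnancies already reported. Section 9.3.6 makes a spontaneously reported pregnancy in the course of the trial reportable, including in a male participant's partner, with no day count. Table 14 note b (Appendix 6) asks for added condom use for at least 120 days if study treatment may weaken hormonal contraception.

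**The concern.** A restart rule should not become looser as the event becomes worse. Here full dosing can resume at a grade that has its own row, and that row calls for a hold. Table 7 does not say which row governs once such a participant is back on drug at Grade 2. The Grade 3 row then returns the participant to the routine eye schedule, which is every 8 weeks after Cycle 2 Day 1 (Section 9.5.1.3), whereas a Grade 1 event is rechecked within 10 days.

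Grade 2 retinal toxicity matters at doses used in this trial. Section 5.5.1.1.2 describes a Japanese Phase I study in which two participants at 45 mg BID had recurrent Grade 2 detachment of the retinal pigment epithelium. That study counted these as DLTs because they recurred at the same grade on a reduced dose, and it declared 45 mg BID its MTD.

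On pregnancy, Section 3.2.1.2.1 reports embryo deaths in rats and rabbits and malformations in rabbits with binimetinib, which Cohorts A, C and E receive. A site that learns of a pregnancy after the Section 9.3.1 window but within the contraception period finds one section that says the duty has ended and another that implies it continues.

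**Working it through.** The plan states no figure to reproduce. The check sets the rules side by side and subtracts day counts.

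**Step 1. Same residual grade, different starting grade.** Take two participants who are both at Grade 2 on day 7 of the hold, with a baseline below Grade 2.

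| | Began at Grade 3 | Began at Grade 2 |
|---|---|---|
| Day 7, Grade 2 | restart at current dose | still on hold |
| Day 10, still Grade 2, had been on 45 mg BID | on 45 mg BID | restart at 30 mg BID |
| Day 10, still Grade 2, had been on 30 mg BID | on 30 mg BID | discontinue |

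The dose ratio at the upper level is 45 / 30 = 1.5. At the lower level the contrast is continue against stop.

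**Step 2. Is this a general pattern in Table 7?** Nine event types have instructions for both Grade 2 and Grade 3: retinal, other eye, AST/ALT (compared at the same bilirubin level), CK, rash, diarrhea, nausea/vomiting, pneumonitis, and all other. Several keep the dose after Grade 3:

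- AST/ALT with bilirubin ≤2 × ULN uses the same threshold in the Grade 2 and Grade 3 rows: Grade ≤1, or Grade ≤2 with liver metastasis.
- CK without renal impairment: "If asymptomatic, maintain dose of binimetinib. Monitor closely and measure isoenzymes and myoglobin in blood and urine". Grade 2 CK also continues at the same dose.
- First Grade 3 rash: "Resume treatment with binimetinib at the same dose level", but only after improvement to Grade ≤1, as for Grade 2 rash when it is interrupted.

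The retinal rows are the only ones (1 of 9) in which the Grade 3 row allows a current-dose restart at a higher residual grade than the Grade 2 row.

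**Step 3. Does the DLT process catch it?** Confirmed Grade ≥3 retinopathy or retinal detachment is a DLT (Section 5.1.3), and continuing then requires discussion with the sponsor. The DLT period is 21 days in Cohort A and 28 days in Cohorts C and E. Treatment can run for 35 cycles × 21 days = 735 days. So 21 / 735 = 2.9% or 28 / 735 = 3.8% of the maximum treatment time is covered.

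**Step 4. Pregnancy windows.**

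- 180 − 120 = 60 days of required contraception after the Section 9.3.1 window closes (120 / 180 = 67% covered).
- 180 − 30 = 150 days if new anticancer therapy starts (30 / 180 = 17% covered).
- Section 9.3.6 has no day count. Section 5.3 ends the trial at the last participant's final contact, and Section 9.10.3.5 keeps survival contact about every 12 weeks. Days 30 to 180 after a participant's last dose would therefore usually fall within the trial.

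**The case against.** *The retinal rows have a logic.* Each rewards improvement by one grade, and the worse event has the shorter clock (7 against 10 days). That explains each row alone. It does not explain why, at the same residual grade, the worse event gets the higher dose.

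*Grade 2 is not a bar to dosing.* The Grade 2 row itself restarts an unresolved event, at a reduced dose. This stands: the dispute is about dose level, or stopping at 30 mg BID.

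*Residual Grade 2 after Grade 3 is accepted elsewhere.* It is, for AST/ALT with liver metastasis, but there the Grade 2 row gives the same allowance.

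*Clinicians have discretion.* Table 7 is a guideline, a participant who does not tolerate 45 mg BID may drop to 30, treatment may be stopped for any untoward effect (Section 8.1), and eye examinations may be more frequent (Section 9.5.1.3). This reduces the practical risk and leaves the written rule as it is.

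*No harm is shown.* Correct. The documents do not measure the effect of a restart at Grade 2, and the ocular signal in the other Phase I study described in Section 5.5.1.1.2 arose at 60 mg BID, above this trial's 45 mg maximum.

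*Pregnancy is handled in Section 9.3.6.* Largely so. Drug-related SAEs also remain reportable at any time, and pregnancy losses and congenital anomalies count as serious. What remains is a conflict with the only window that has dates.

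**Conclusion.** Both misalignments are in the current text. In Table 7 the worse retinal event has the looser rule for restart at the current dose. In Sections 9.3.1 and 9.3.6 the protocol gives two pregnancy-reporting rules that disagree for up to 60 days, or up to 150 days with new anticancer therapy, of the minimum contraception period. Neither affects DLT evaluation, RP2D selection, ORR or sample size.

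Four stronger readings are tempting and are not supported:

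- A reader might infer that the protocol treats Grade 2 retinal toxicity as dose-limiting. Grade 2 requires a hold, but Section 5.1.3 makes retinopathy or retinal detachment a DLT only from Grade 3; retinal vein disorder is listed separately.
- A reader might size the problem from the 19% ocular event rate in Section 3.2.1.2.2. That figure counts any ocular event of any grade on single-agent binimetinib and says nothing about this row. The same section reports one treatment-related Grade ≥3 retinal vascular disorder with binimetinib 30 or 45 mg BID plus mFOLFOX7; if that was a vein occlusion, Table 7 requires discontinuation and this row would not apply. The number affected is unknown, probably very small and possibly zero.
- A reader might infer that pregnancies after day 120 go unreported. Section 9.3.6 usually reaches them while the trial is open.
- A reader might infer that Table 14 note b shortens contraception to 120 days. It is a conditional minimum, and Appendix 6 defers to the time frame in Section 6.1.

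The conclusion rests on sites applying the rows as written.

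**What to change.** **Table 7, retinal Grade 3 row.** Restart at the current dose only at baseline or Grade ≤1 within 7 days. If Grade 2 at day 7, keep holding and apply the Grade 2 row: current dose if at baseline or Grade ≤1 by day 10 from interruption, otherwise a reduced dose, or discontinue if already at 30 mg BID. Leave the steps for an event still Grade 3 at day 7 unchanged; their longest hold is 7 + 10 = 17 days, under the 21-day limit.

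*Cost:* up to 10 − 7 = 3 more days on hold for those at Grade 2 on day 7, and a few more reductions (permanent, given the bar on re-escalation) or discontinuations at 30 mg BID.

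**Pregnancy.** Set the window in Section 9.3.1 and Table 10 to 180 days after treatment stops, regardless of new anticancer therapy, and refer to it in Section 9.3.6.

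*Cost:* a few more reports.

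**Optional tidy-up.** Change Table 14 note b from 120 to 180 days.
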